14 PUBLICATION

Authorship of publications from data generated in study will be determined based on the uniform requirements for manuscripts submitted to biomedical journals (as outlined in the International Committee of Medical Journal Editors December 2013) which states:

- Authorship should be based on
 - Substantial contributions to the conception or design of the work, acquisition of data, analysis, or interpretation of data for the work AND
 - Drafting the article or revising it critically for important intellectual content; AND
 - Final approval of the version to be published; AND
 - Agreement to be accountable for all aspects of the work in ensuring that questions related to the accuracy or integrity of any part of the work re appropriately investigated or resolved

When a large, multicenter group has conducted the work, the group will identify the individuals who accept direct responsibility for the manuscript. This individual will fully meet the criteria for authorship defined above.

Funding, collection of data or general supervision of the research alone or in combination does not qualify an individual for authorship.

Any publication, in any form, that is derived from this study must be submitted to CaNVAS for review and approval. The study contract between the institution, principal investigator, Co-investigator and CaNVAS or its delegate will outline the requirements for publication review.

APPENDIX I: PERFORMANCE SCORES

Karnofsky Performance Scale For Patients 16 Years and Older	
Percent	Description
100	Normal, no complaints, no evidence of disease.
90	Able to carry on normal activity; minor signs of symptoms of disease.
80	Normal activity with effort; some signs of symptoms of disease.
70	Cares for self, unable to carry on normal activity or to do active work.
60	Requires occasional assistance but is able to care for most of his/her needs.
50	Requires considerable assistance and frequent medical care.
40	Disabled, requires special care and assistance.
30	Severely disabled, hospitalization indicated. Death not imminent.
20	Very sick, hospitalization indicated. Death not imminent.
10	Moribund, fatal processes progressing rapidly.
0	Dead

Lansky Performance Scale For Patients Less Than 16 Years of Age	
Lansky Score	Play Score
100	Fully active, normal
90	Minor restrictions in physically strenuous activity
80	Active, but tires more quickly
70	Both greater restriction of and less time spent in play activity
60	Up and around, but minimal active play; keeps busy with quieter activity
50	Gets dressed but lies around much of the day, no active play but able to participate in all quiet play and activities
40	Mostly in bed ; participate in quiet activities
30	In bed ; needs assistance even for quiet play
20	Often sleeping, play entirely limited to very passive activities
10	No play; does not get out of bed
0	Unresponsive

APPENDIX II: DOSING NOMOGRAM

Trametinib dosing will be weight based. The drug is supplied in tablet form or in oral solution form. Dosing nomogram for tablet formulation below. **The maximum dose is 2 mg per day.**

Note: If switching from trametinib solution to trametinib tablets or vice versa in subjects requiring dose reduction, match up the subject's starting dose to ensure the proper dose reduction is being made.

Subject Weight ≥ 35 kg Formulation: Trametinib Tablets 0.5 mg and 2 mg						
Dose Level	Dose Level 1: 0.025 mg/mg/dose once daily Maximum Dose 2 mg Daily			Dose Level -1: 0.020 mg/mg/dose once daily Maximum Dose 1.5 mg Daily		
Weight [#] (kg)	Dose	Number of 0.5 mg Tablets	Number of 2 mg Tablets	Dose	Number of 0.5 mg Tablets	Number of 2 mg Tablets
35 – 50	1 mg	2	0	Oral Solution only 0.75 mg (15 mL)		
50.1 – 70	1.5 mg	3	0	1 mg	2	0
≥ 70.1	2 mg	0	1	1.5 mg	3	0

[#] Weight measured within 7 days of the start of a cycle or pre-determined dosing weight in those subjects whom fluid status fluctuates.

Formulation: Trametinib Oral Solution (0.05 mg/mL)				
Dose Level	Dose Level 1: 0.025 mg/mg/dose once daily Maximum Dose 2 mg Daily		Dose Level -1: 0.020 mg/mg/dose once daily Maximum Dose 1.5 mg Daily	
Weight [#] (kg)	Dose	Volume of Oral Solution	Dose	Volume of Oral Solution
9.0-9.9kg	0.12 (0.0125mg/kg)	2.3mL	0.18mg	3.6mL
10.0-10.9kg	0.2mg	4mL	0.2mg	4mL
11-11.9	0.25mg	5mL	0.22mg	4.4mL
12-13.9	0.3mg	6mL	0.24mg	4.8mL
14-15.9	0.35mg	7mL	0.28mg	5.6mL
16-17.9	0.4mg	8mL	0.32mg	6.4mL
18-19.9	0.45mg	9mL	0.36mg	7.2mL
20-22.9	0.5mg	10mL	0.4mg	8mL
23-24.9	0.6mg	12mL	0.46mg	9.2mL
25-29.9	0.7mg	14mL	0.5mg	10mL
30-34.9	0.8mg	16mL	0.6mg	12mL
35 – 50	1 mg	20 mL	0.75 mg	15 mL
50.1 – 70	1.5 mg	30 mL	1 mg	20 mL
≥ 70.1	2 mg	40 mL	1.5 mg	30 mL

Weight measured within 7 days of the start of a cycle or pre-determined dosing weight in those subjects whom fluid status fluctuates.

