2 RATIONALE

2.1 Investigational drug: Trametinib (Mekenist®)

Trametinib is a reversible, highly selective allosteric inhibitor of MEK1/MEK2 activation and kinase activity. Trametinib interferes with cellular signal-transduction and inhibits cell proliferation by inducing apoptosis in tumor cell lines in vitro and human tumor xenografts in mice. Trametinib has demonstrated anti-proliferative activity against a broad range of tumor cell lines and xenograft models, and the activity of trametinib was most pronounced in human tumor models harboring BRAF-activating variants. Trametinib inhibits ERK phosphorylation leading to Gap-1 (G1) cell cycle arrest and tumor xenograft growth inhibition in vivo following oral dosing.

Subjects will receive oral trametinib daily in continuous 28-day cycles at 0.025 mg/kg/day with a maximum dose of 2 mg. A single dose reduction will be permitted in individual subjects who experience toxicity while still having evidence of clinical benefit and is assessed per the investigator.

This trial will enroll subjects with symptomatic vascular anomalies with causative variants of the Ras/MAPK pathway and evaluate objective response using individualized subject response criteria. Subjects will also be evaluated for toxicity using CTCAE v5.0. Stopping rules for toxicity and response are included in the statistical section.

Trametinib is a MEK inhibitor with safety data in children and adults with promising pre-clinical and clinical data supporting efficacy in subjects with VA and CLA.^{10-12,14,17,29,34,44,45} In summary, this Phase II, non-randomized, interventional, open-label, sub-protocol of the VATCH trial provides trametinib to subjects with Ras/MAPK pathway driven vascular anomalies. This protocol represents the first collaborative multicenter trial for the targeted treatment of children and young adults with vascular anomalies driven by Ras/MAPK pathway activation.

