4.3.1 Dosing

Eligible subjects will be treated with trametinib administered at 0.025 mg/kg/dose (or 0.0125mg/kg/dose for critically ill subjects, infants < 10kg at enrollment, or based on clinical discretion) daily given orally by tablet or by oral solution via a nasogastric tube (NGT) or gastric tube (GT) at dose level 1 for each disease strata. Dosing will be daily on a continuous 28-day cycle, for up to 24 total cycles. Dosing will be based on weight in kilograms (kg) obtained within 7 days of starting each cycle or pre-determined dosing weight in those subjects whom fluid status fluctuates. The total daily trametinib dose should not exceed the adult dose (2mg) in any subject.

Refer to [Section 10](#) for dose modifications for toxicity.

Trametinib formulations include:

Powder for oral solution: The liquid concentration is 0.05 mg/mL. Doses of trametinib oral solution will be rounded to nearest 0.1mL (0.005 mg) for doses ≤ 0.11 mg (in oral syringes ≤ 3 mL), 0.2 mL (0.01mg) for doses > 0.11 mg (in oral syringes of 5-10 mL volume). Trametinib pediatric oral solution formulation will be administered with a graduated syringe.

Tablet formulation: Doses of tablet formulation should be rounded to the nearest 0.5mg. It is recommended that subjects drink 4 to 6 mL of water/kg body weight following dosing.

A dosing nomogram ([see Appendix II](#)) based on weight and dose level will be used to prescribe trametinib to minimize inter-subject dosing variability. If vomiting occurs after taking the oral solution formulation, the dose should not be repeated, and next dose given at its scheduled time.

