10.2.3 Dose Modifications for Non-Hematologic Toxicity

If a subject experiences a dose-modifying non-hematologic toxicity as defined in [Section 10.2.1](#), the treatment will be held.

If the toxicity does not resolve to meet inclusion/exclusion parameters or baseline within 14 days of drug discontinuation the subject must be removed from protocol therapy unless specifically documented in toxicities of special interest [Section 10.2.6](#).

If the toxicity resolves to meet inclusion/exclusion parameters or baseline within 14 days of drug discontinuation the subject may resume treatment with a reduction to the next lower dose according to [Appendix II](#). See [Appendix II](#) for dosing modification in subjects receiving oral solution or the specified dose reduction in subjects receiving tablets.

- Doses reduced for toxicity will not be re-escalated, even if there is minimal or no toxicity with the reduced dose, unless otherwise specified in the toxicities of special interest [Section 10.2.6](#).
- If the same dose-modifying toxicity recurs in a subject who has resumed treatment, the subject must be removed from protocol therapy.

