APPENDIX IV: MEDICATION DIARY (ORAL SOLUTION)

Complete each day with the date, time and volume in mL of trametinib oral solution taken. Make note of other drugs and supplements taken. Your doctor will tell you what foods you should avoid. Trametinib should be taken by mouth on an empty stomach once a day, at least 1 hour before or 2 hours after a meal. Do not take a missed dose of trametinib within 12 hours of the next scheduled dose. If vomiting occurs after taking oral solution formulation, the dose should NOT be repeated and the next dose should be administered at the regularly scheduled time. Return the completed diary to your institution at the end of each treatment cycle. Please return all unused solution at the end of each cycle. Store the solution at room temperature (25°C or 77°F).

Immediately prior to the removal of dose for administration swirl the bottle of solution gently 2-3 times, if any foam appears allow the bottle to sit for at least 1 minute for the foam to dissipate. Remove the required dose using a suitable graduated syringe:

- a. Ensure that the syringe plunger is fully pushed into the barrel.
- b. Insert the syringe tip into the Adapter, then invert the bottle and dispense at least 5 mL of solution into the syringe and then pump the entire solution back into the bottle to purge the syringe of any air bubbles. Repeat this step until the syringe is free from air bubbles.
- c. Withdraw the required dosing volume. Then re-invert the bottle and remove the syringe from the Adapter and administer the dose to the subject as soon as possible.

Sites will fill out the cycle, dates and the volume of prescribed solution per day per [Appendix II](#).

Trametinib in the Treatment of _____

Cycle _____	

 Patient Name	

 DOB
-------------	--	---

Drug	Dosage	Route	Day
Trametinib			

Date Due	Date Received	Week	Day	Dose given	Comments
		1	1		
			2		
			3		
			4		
			5		
			6		
			7		
		2	8		
			9		
			10		
			11		
			12		
			13		
			14		

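### Appendix II oral-solution table: the Dose Level 1 entry for 11-11.9 kg (0.25 mg) is 9% to 16% below the labelled 0.025 mg/kg at every weight in the band, which shrinks the single permitted reduction to 12%

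*Protocol*

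**What the plan says.** Section 4.3.1 sets the starting dose at 0.025 mg/kg once daily, with a 0.0125 mg/kg alternative for critically ill subjects, infants under 10 kg, or at clinical discretion. It gives the solution strength as 0.05 mg/mL and rounds solution doses to "0.2 mL (0.01mg) for doses > 0.11 mg". It also says that a nomogram "based on weight and dose level will be used to prescribe trametinib to minimize inter-subject dosing variability".

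That nomogram is Appendix II. Its oral-solution table has one fixed dose per weight band in each of two columns, "Dose Level 1: 0.025 mg/mg/dose once daily" and "Dose Level -1: 0.020 mg/mg/dose once daily". The row for 11-11.9 kg reads 0.25 mg (5 mL) at Level 1 and 0.22 mg (4.4 mL) at Level -1.

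The table is used directly in dosing. For the medication diary, Appendix IV states "Sites will fill out the cycle, dates and the volume of prescribed solution per day per" Appendix II. After a dose-modifying non-hematologic toxicity that resolves in time, Section 10.2.3 states that "the subject may resume treatment with a reduction to the next lower dose according to" Appendix II. Section 2.1 says "A single dose reduction will be permitted in individual subjects who experience toxicity", and Section 10.2.3 adds: "If the same dose-modifying toxicity recurs in a subject who has resumed treatment, the subject must be removed from protocol therapy".

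**The concern.** A banded dose normally equals the labelled mg/kg at some weight within its band and deviates modestly on either side. At 11-11.9 kg the Level 1 dose lies below its label even at the lightest weight, so every child in the band starts under the intended dose.

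The same cell also determines the size of the toxicity step. With Level 1 too low and Level -1 where its label puts it, the gap between them narrows. A child in this band gets a smaller reduction than a child one band heavier. Under Section 10.2.3 that reduction is in general not reversed, and recurrence of the same toxicity ends protocol therapy.

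Section 2.1.1 adds context. It reports that more than half of the children under 6 years treated at 0.025 mg/kg in a pediatric oncology study had trough levels below the adult target. Assuming most children of 11-11.9 kg are under 6, this row lowers the dose further in a group whose exposure the protocol already describes as low.

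**Working it through.** **Inputs.** Labels of 0.025 and 0.020 mg/kg, and the row doses, from the Appendix II oral-solution table. Solution strength of 0.05 mg/mL and the 0.2 mL (0.01 mg) rounding step from Section 4.3.1.

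**Step 1: the row agrees with its own volumes.** 5 mL x 0.05 = 0.25 mg and 4.4 mL x 0.05 = 0.22 mg. Dose and volume match, so a misprinted volume is not the explanation.

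**Step 2: delivered dose per kg = dose / weight; cut = 1 - (Level -1 / Level 1).**

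| Band (kg) | Level 1 (mg) | Level 1 mg/kg, low to high edge | Reaches 0.025? | Level -1 (mg) | 0.020 x low edge (mg) | Cut |
|---|---|---|---|---|---|---|
| 11-11.9 | 0.25 | 0.0227-0.0210 | No | 0.22 | 0.22 | 12.0% |
| 12-13.9 | 0.30 | 0.0250-0.0216 | Yes | 0.24 | 0.24 | 20.0% |
| 14-15.9 | 0.35 | 0.0250-0.0220 | Yes | 0.28 | 0.28 | 20.0% |
| 16-17.9 | 0.40 | 0.0250-0.0223 | Yes | 0.32 | 0.32 | 20.0% |
| 18-19.9 | 0.45 | 0.0250-0.0226 | Yes | 0.36 | 0.36 | 20.0% |
| 20-22.9 | 0.50 | 0.0250-0.0218 | Yes | 0.40 | 0.40 | 20.0% |
| 23-24.9 | 0.60 | 0.0261-0.0241 | Yes | 0.46 | 0.46 | 23.3% |
| 25-29.9 | 0.70 | 0.0280-0.0234 | Yes | 0.50 | 0.50 | 28.6% |
| 30-34.9 | 0.80 | 0.0267-0.0229 | Yes | 0.60 | 0.60 | 25.0% |

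**Step 3: shortfall at 11-11.9 kg.** 0.25/11 = 0.0227, and 0.0227/0.025 is 9.1% low. 0.25/11.9 = 0.0210, which is 16.0% low.

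**Step 4: what the label and the rounding rule would give.** 0.025 x 11 = 0.275 mg at the low edge and 0.025 x 11.9 = 0.298 mg at the high edge. The five rows from 12 to 22.9 kg all use the low edge. On that basis 0.275 mg (5.5 mL) lies midway between 0.27 mg (5.4 mL) and 0.28 mg (5.6 mL). Rounding to 0.01 mg cannot bring it to 0.25 mg. The value 0.25 mg equals 0.025 x 10 kg, which is consistent with a slip of one row; that is an inference.

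**Step 5: with 0.28 mg.** 0.28/11 = 0.0255 (+1.8%) and 0.28/11.9 = 0.0235 (-5.9%), so 0.025 mg/kg now falls inside the band. Cut: 1 - 0.22/0.28 = 21.4%. Volume: 0.28/0.05 = 5.6 mL, a multiple of 0.2 mL and already in the table as the Level -1 volume at 14-15.9 kg. The column still rises to 0.30 mg in the next band.

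**The case against.** The strongest case against the point has four parts.

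- **The deviation is not unusual in size.** The table accepts -13.7% at 13.9 kg (0.30/13.9 = 0.0216) and -20% at 50 kg (1/50 = 0.0200). This is true, but those are upper-edge deviations in bands whose lower weights reach or exceed the label. At 11-11.9 kg the whole band is below it.
- **Level 1 may have been rounded to whole millilitres.** Every Level 1 volume from 10 kg up is a whole number, so 5.5 mL would become 5 or 6 mL. That could explain how the cell arose. It is not the rule in Section 4.3.1, which allows 0.2 mL steps in syringes of 5-10 mL.
- **Half the labelled dose is allowed anyway.** Section 4.3.1 permits a 0.0125 mg/kg start at clinical discretion. That is a deliberate choice for an individual. It does not make a column labelled 0.025 correct.
- **No text requires a 20% step.** This stands. Section 10.2.3 asks only for the next lower dose in Appendix II, so the 12% cut breaks no stated rule in itself. It is the consequence of a Level 1 cell that misses its label.

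From the cuts of 23%, 29% and 25% at 23-34.9 kg, a reader might infer that those rows are wrong as well, or that the reduction must be 20% throughout. The protocol does not support this. Level 1 in those rows spans 0.025 mg/kg within each band, and Level -1 is exactly 0.020 x the lower band edge, as in every solution row from 9 to 34.9 kg. The rows from 35 kg up give 25% to 33%. Forcing 20% by raising Level -1 to 0.48, 0.56 and 0.64 mg would put doses given after toxicity above 0.020 mg/kg, by as much as 12% at 25 kg (0.56/25 = 0.0224).

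**Conclusion.** One cell of the table is wrong against its own label. Level 1 at 11-11.9 kg is 9.1% to 16.0% low, and the stated rounding rule does not account for it. The consequence is a 12% reduction where the five bands from 12 to 22.9 kg give 20%.

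The conclusion rests on reading mg/mg as mg/kg, which Section 4.3.1 confirms for Level 1, and on taking the column label as the intended dose. The point is small: it concerns a 1 kg band, and the number of subjects who will fall in it is unknown. A reader might infer harm to the response or toxicity results. The protocol gives no exposure-response data for this population, so no such effect can be claimed. The case for correcting it is that sites prescribe from this cell.

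**What to change.** In the Appendix II oral-solution table, change Level 1 at 11-11.9 kg from 0.25 mg (5 mL) to 0.28 mg (5.6 mL), with confirmation by the sponsor and pharmacy. Leave Level -1 at 0.22 mg. Correct the column unit from mg/mg to mg/kg. Leave the rows from 23 to 34.9 kg as they are.

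The cost is an amendment of one row and the column labels. The starting dose in this band rises by 0.03 mg a day (0.28/0.25 = 1.12, or 12% over the present entry) and sits 1.8% above the label at 11 kg. The reduced dose does not change.

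The two rows below need a separate look in the same amendment. At 10.0-10.9 kg both levels are 0.2 mg. At 9.0-9.9 kg the Level 1 column holds the 0.0125 mg/kg start (0.12 mg), below the 0.18 mg listed at Level -1.

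### In the oral-solution nomogram the reduced dose is 50% above the starting dose at 9.0–9.9 kg and equal to it at 10.0–10.9 kg

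*Protocol*

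**What the plan says.** Appendix II tabulates oral-solution doses by body weight at two levels, headed "Dose Level 1: 0.025 mg/mg/dose once daily" and "Dose Level -1: 0.020 mg/mg/dose once daily". The unit is evidently meant to be mg per kg. The two lightest rows read:

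- 9.0–9.9 kg: Level 1 is "0.12 (0.0125mg/kg"), 2.3 mL; Level -1 is 0.18 mg, 3.6 mL.
- 10.0–10.9 kg: Level 1 is 0.2 mg, 4 mL; Level -1 is 0.2 mg, 4 mL.

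Section 4.3.1 makes this nomogram the prescribing tool. Besides the standard 0.025 mg/kg it allows "0.0125mg/kg/dose for critically ill subjects, infants < 10kg at enrollment, or based on clinical discretion". Appendix IV tells sites to fill in the daily volume from Appendix II.

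For toxicity, Section 10.2.3 says that once the event has resolved "the subject may resume treatment with a reduction to the next lower dose according to" Appendix II, and it names that appendix as the source "for dosing modification in subjects receiving oral solution or the specified dose reduction in subjects receiving tablets". The rules for hematologic toxicity (10.2.4), rash (10.2.6.1 and 10.2.6.3), retinal pigment epithelial detachment (10.2.6.8) and hypertension (10.2.6.11) also cite Appendix II. Those for CK elevation, pneumonitis and diarrhea reach it through 10.2.3.

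**The concern.** A reduced dose level has to lie below the level it replaces. In two rows it does not. A child who has just had a dose-modifying toxicity on the printed starting dose would restart on more drug, or on the same amount, under the label of a reduction.

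Other rules make this worse. Section 10.2.3 takes a subject off therapy if the same toxicity recurs after restart, so a child re-exposed to a higher dose could lose the treatment for that reason. For Grade 2 rash, Section 10.2.6.3 lowers the dose and returns to the previous level on recovery; in the 9.0–9.9 kg row that sequence runs backwards.

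Safety is a primary objective, and the data suffer too. A dose-reduction record for such a child would describe a step that did not happen, and any summary of toxicity by dose level would be wrong for that child.

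**Working it through.** **Inputs.** Doses and volumes come from Appendix II. The concentration is from Section 4.3.1: "The liquid concentration is 0.05 mg/mL".

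**Step 1: do the milligram and volume columns agree?** Dose = volume × 0.05 mg/mL.

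- 2.3 mL × 0.05 = 0.115 mg (printed 0.12)
- 3.6 mL × 0.05 = 0.18 mg (printed 0.18)
- 4 mL × 0.05 = 0.20 mg (printed 0.2, both levels)

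The two columns support each other, so the entries are not a misread of the table.

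**Step 2: size of the step.** Change = Level -1 / Level 1 − 1.

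| Weight (kg) | Level 1 (mg) | Level -1 (mg) | Change |
|---|---|---|---|
| 9.0–9.9 | 0.12 | 0.18 | +50% |
| 10.0–10.9 | 0.20 | 0.20 | 0% |
| 11–11.9 | 0.25 | 0.22 | −12% |
| 12–13.9 | 0.30 | 0.24 | −20% |
| 14–15.9 | 0.35 | 0.28 | −20% |
| 16–17.9 | 0.40 | 0.32 | −20% |
| 18–19.9 | 0.45 | 0.36 | −20% |
| 20–22.9 | 0.50 | 0.40 | −20% |
| 23–24.9 | 0.60 | 0.46 | −23% |
| 25–29.9 | 0.70 | 0.50 | −29% |
| 30–34.9 | 0.80 | 0.60 | −25% |
| 35–50 | 1.0 | 0.75 | −25% |
| 50.1–70 | 1.5 | 1.0 | −33% |
| ≥ 70.1 | 2.0 | 1.5 | −25% |

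By volume the first row changes by 3.6 / 2.3 − 1 = +57%.

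**Step 3: where the two rows come from.** mg/kg = dose / weight limit.

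- 9.0–9.9 kg, Level 1: 0.12/9.9 to 0.12/9.0 = 0.0121 to 0.0133 mg/kg, the halved start. Level -1: 0.18/9.9 to 0.18/9.0 = 0.0182 to 0.0200 mg/kg, the standard reduced level (0.020 × 9 = 0.18). The row pairs a start from one scheme with a reduction from the other.
- 10.0–10.9 kg, both levels: 0.20/10.9 to 0.20/10.0 = 0.0183 to 0.0200 mg/kg. Level 1 is headed 0.025 but is already at or below 0.020.

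**Step 4: the 0.0125 mg/kg start at other weights.** Section 4.3.1 allows it at clinical discretion at any weight, but no column matches it. At 20 kg the start is 0.0125 × 20 = 0.25 mg and the printed Level -1 is 0.40 mg: 0.40 / 0.25 − 1 = +60%.

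**Step 5: coverage.** Inclusion criterion 2 (Section 5.1) admits subjects from 2 months of age, and Section 4.3.1 expects infants under 10 kg. The first row starts at 9.0 kg, so lighter infants have no entry at either level.

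**The case against.** The best argument is that the Level -1 cell in the 9.0–9.9 kg row is right for a different child. The 0.0125 mg/kg start is optional, and Section 10.1.1 lets critically ill patients who tolerate it move up to 0.025 mg/kg, no later than after three cycles. At 9.0–9.9 kg that is 0.225 to 0.248 mg, and 0.18 mg is then a true cut of 20% to 27%. This is correct, but the table has no cell for that starting dose; the Level 1 dose it does print is the halved one. Section 10.2.6.1 adds that rash can begin in cycle 1 or 2, when a child may still be on the lower start.

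A second argument is that Section 10.2.3 asks for a lower dose, so a careful site would not give 0.18 mg after 0.12 mg. It is fair to say that rule and table contradict each other. But the site would then have nothing to follow: the Protocol names no dose level below 0.0125 mg/kg, and the 10.0–10.9 kg row offers no lower cell.

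Some smaller points stand and limit the finding:

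- Not every reduction is routed to Appendix II. The LVEF rule (10.2.6.5) names no source for its reduced dose, and hepatic toxicity (10.2.5) cites a Section 10.1.3 that the Protocol does not contain.
- Starting doses below 9 kg can be worked out from the mg/kg dose and the rounding rule in 4.3.1. What is undefined there is the reduced dose.
- The diary in Appendix IV asks for the daily volume, so the dose actually taken can be recovered for analysis.
- The wrong dose of 0.018 to 0.020 mg/kg is still below the standard 0.025 mg/kg. This limits the absolute exposure but does not justify raising a dose after toxicity.

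**Conclusion.** The point holds and must be fixed. For a subject on the printed Level 1 dose, the labelled reduction is +50% by milligrams (+57% by volume) at 9.0–9.9 kg and 0% at 10.0–10.9 kg. The 12 heavier rows are true reductions. No reduced level exists for the 0.0125 mg/kg start, in these rows or elsewhere.

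This rests on reading the column unit as mg per kg and on the subject being on the printed Level 1 dose at the time of toxicity. The Protocol gives no expected weight distribution, so the number of subjects affected is unknown. The contradiction does not depend on that number.

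**What to change.** The clinical and pharmacy leads should reconcile Appendix II with Sections 4.3.1 and 10.2.3 before any subject under 11 kg is dosed from the table:

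- In every row, the Level -1 cell lies below the Level 1 cell.
- Every permitted starting level, including 0.0125 mg/kg at any weight, has its own reduced level or an explicit instruction to stop.
- Every admissible weight, including below 9.0 kg, has an entry or a stated calculation rule.
- The column unit reads mg/kg, and the Level 1 entry at 10.0–10.9 kg is either brought to its heading or explained.

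The doses are a clinical and pharmacy decision, and none is proposed here. The cost is a corrected appendix and a safety letter to sites. Sample size and the efficacy analysis are unaffected.

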10 DOSE MODIFICATION AND MANAGEMENT OF ADVERSE EVENTS

10.1 Dose Modifications

10.1.1 Dose Escalation

Patients with critical illness may be initiated at starting dose of 0.0125 mg/kg with approval of study chair or co-chair. If in the opinion of the site investigator this dose is tolerated may then increase to the standard 0.025 mg/kg dosing. This should take place no later than after 3 cycles of treatment.

0.032 mg/kg dosing: Prior Oncologic dosing in patients less than 6 years of age has demonstrated tolerability in those populations at 0.032 mg/kg dosing. Escalation to 0.032 mg/kg dosing prior to completion of 6 cycles of treatment only after approval of study chair or co-chair.

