10.2.4 Dose Modifications for Hematologic Toxicity

The study chair must be notified for any dosage modification or use of myeloid growth factors.

- If a subject experiences a dose modifying hematologic toxicity as defined in [Section 10.2.2](#), the treatment will be held until improvement to Grade 3 or less.
- Subjects will be allowed 1 episode of Grade 4 hematologic toxicity without dose reduction.
- If there is > 1 hold for Grade 4 hematologic toxicity, dose will be reduced per guidance in [Appendix II](#). Counts should be checked twice weekly during this time.
- Doses reduced for toxicity will not be re-escalated, even if there is minimal or no toxicity with the reduced dose.
- If dose-modifying toxicity recurs in a subject who has resumed treatment at the reduced dose, the subject must be removed from protocol therapy.

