
Grade 2 and Grade 3:
 
Symptomatic with mild to moderate decrease in visual acuity; limiting instrumental ADL
	
Consult ophthalmologist immediately
	
For RPED and RVO:
 
 ▪ Hold treatment. ▪ If RPED and RVO excluded: restart treatment at same dose level. ▪ If RPED diagnosed: see RPED dose modification table below (following this table); report as SAE. ▪ If RVO diagnosed: permanently discontinue treatment and report as SAE. 
For uveitis:
 
 ▪ Hold treatment.

Grade 4:
 
Sight threatening consequences; urgent intervention indicated; best corrected visual acuity of 20/200 or worse in the affected eye
	
Consult ophthalmologist immediately
	
Interrupt treatment.
 
 ▪ If RPED and RVO excluded: consider restarting treatment at the same or reduced dose level, after discussion with study chair. ▪ If RVO or RPED diagnosed: permanently discontinue treatment and report as SAE.

Mandatory dose modification and recommended clinical management for retinal pigment epithelial detachments (RPED suspected to be related to trametinib treatment)

Retinal Detachment (NCI CTCAE v5.0)	Recommended Management Guidelines	Dose Modification Requirement
Grade 1–2: (Asymptomatic; clinical or diagnostic observations only)	Retinal evaluation monthly.	
 Continue treatment with retinal evaluation monthly until resolution. If RPED worsens, follow instructions below.
Grade 3–4: (Symptomatic with mild to moderate decrease in visual acuity; limiting instrumental ADL)	Retinal evaluation monthly.	
 Hold treatment. If improved to \leq Grade 1, restart treatment at reduced dose (to the next lower dose according to Appendix II). If no recovery within 4 weeks permanently discontinue trametinib treatment

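### In two of the 14 oral-solution rows of Appendix II, Dose Level -1 is not lower than the printed Level 1 dose: +50% at 9.0-9.9 kg and 0% at 10.0-10.9 kg

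*Protocol*

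**What the plan says.** Appendix II lists two dose levels. Level 1 is headed 0.025 and the only reduced level is headed "Dose Level -1: 0.020 mg/mg/dose once daily" (the unit is printed as mg/mg and is read here as mg/kg). In the oral-solution table, the 9.0-9.9 kg row gives Level 1 as "0.12 (0.0125mg/kg", 2.3 mL, and Level -1 as 0.18 mg, 3.6 mL. The 10.0-10.9 kg row gives 0.2 mg, 4 mL, at both levels.

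Section 4.3.1 makes the nomogram the prescribing tool. It sets 0.025 mg/kg as the usual start and allows 0.0125 mg/kg for critically ill subjects, "infants < 10kg at enrollment, or based on clinical discretion". Section 10.1.1 adds, for one of these groups, that "Patients with critical illness may be initiated at starting dose of 0.0125 mg/kg with approval of study chair or co-chair". Of the later increase to 0.025 mg/kg it says: "This should take place no later than after 3 cycles of treatment".

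The toxicity rules send the site to the same appendix:
- Section 10.2.3 (non-hematologic): "the subject may resume treatment with a reduction to the next lower dose according to" Appendix II.
- Section 10.2.4 (hematologic): "dose will be reduced per guidance in" Appendix II.
- Section 10.2.6.8 (retinal detachment, Grade 3-4): "restart treatment at reduced dose (to the next lower dose according to" Appendix II.
- The rash table in 10.2.6.3 and Arm 3 of the hypertension algorithm in 10.2.6.11 refer there as well.

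Section 2.1 permits one dose reduction per subject.

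**The concern.** A reduced dose level has to be lower than the dose it replaces. In two rows it is not, so the text of the toxicity rules and the table they cite contradict each other. The text asks for a lower dose and the cell offers a higher or an equal one. The rows concerned cover the lightest children in the table, and infants under 10 kg are a group for whom 4.3.1 names the low start.

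The gap is wider than the 9.0-9.9 kg row. Anyone started at 0.0125 mg/kg has only 0.020 mg/kg as the printed reduced level, which is above the starting rate. For critically ill subjects, 10.1.1 makes the low dose a lead-in, so the gap falls mainly in the first 3 cycles. Sections 2.1.1 and 4.3.1 set no such limit for infants under 10 kg or for a low start chosen at clinical discretion. Section 10.2.6.1 says that rash can begin in cycle 1 or 2, so even a short lead-in is exposed.

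**Working it through.** **Inputs.** Level 1 and Level -1 doses and volumes are from the Appendix II oral-solution table. The header rates are 0.025 and 0.020 mg/kg. The concentration, 0.05 mg/mL, and the rounding rule (nearest 0.1 mL up to 0.11 mg, nearest 0.2 mL above it) are from 4.3.1.

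**Is this a reading artefact?** Dose = volume x 0.05:
- 3.6 x 0.05 = 0.18 mg, as printed.
- 4 x 0.05 = 0.20 mg, as printed at both levels.
- 2.3 x 0.05 = 0.115 mg, printed as 0.12.

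Dose and volume agree apart from that rounding, so the cells are as the plan intends them to read.

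**Change from Level 1 to Level -1** = (Level -1 / Level 1) - 1:

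| Weight (kg) | Level 1 (mg) | Level -1 (mg) | Change |
|---|---|---|---|
| 9.0-9.9 | 0.12 | 0.18 | +50.0% |
| 10.0-10.9 | 0.2 | 0.2 | 0.0% |
| 11-11.9 | 0.25 | 0.22 | -12.0% |
| 12-22.9 (five rows) | 0.3 to 0.5 | 0.24 to 0.4 | -20.0% each |
| 23-24.9 | 0.6 | 0.46 | -23.3% |
| 25-29.9 | 0.7 | 0.5 | -28.6% |
| 30-34.9 | 0.8 | 0.6 | -25.0% |
| 35-50 | 1 | 0.75 | -25.0% |
| 50.1-70 | 1.5 | 1 | -33.3% |
| 70.1 and over | 2 | 1.5 | -25.0% |

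By volume the 9.0-9.9 kg change is 3.6/2.3 - 1 = +56.5%. That figure leans on the 2.3 mL cell, which is itself doubtful: the dose is above 0.11 mg, so the volume should be a multiple of 0.2 mL, and 2.4 mL is exactly 0.12 mg.

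**Which cell is off the header rate?**
- Level -1 reproduces in both rows at the lower weight limit: 0.020 x 9.0 = 0.18 mg and 0.020 x 10.0 = 0.20 mg.
- Level 1 does not. At 9.0-9.9 kg, 0.025 mg/kg gives 0.225 to 0.248 mg. The printed 0.12 mg matches only its own label (0.0125 x 9.0 to 9.9 = 0.113 to 0.124 mg).
- At 10.0-10.9 kg, 0.025 mg/kg gives 0.250 to 0.2725 mg. The printed 0.2 mg is 20.0% to 26.6% below that and equals the Level -1 rate at 10 kg.

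**When is 0.18 mg a true reduction?** From 0.025 mg/kg: 0.18/0.225 - 1 = -20% at 9.0 kg, and 0.18/0.2475 - 1 = -27% at 9.9 kg. The row prints no 0.025 mg/kg dose. From the low start, the change in nominal rate is 0.020/0.0125 - 1 = +60%.

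**The case against.** The operative text asks for a lower dose. To give 3.6 mL in place of 2.3 mL, a site would have to follow the cell against that wording and against the 0.0125 mg/kg label beside it. Many would query the study chair or stop treatment. Section 2.1.1 makes the low start optional, so an infant under 10 kg may start at 0.025 mg/kg, and for that infant 0.18 mg is a sound cut. The 0.2 mg start at 10.0-10.9 kg could be a deliberate bridge from the half-dose row. The weight bands are narrow, and no endpoint, power figure or analysis changes.

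Most of this stands and limits the consequence to something that could happen. It does not rescue the table. The text directs the site to an appendix that prints no lower dose in these two rows, and an intended 0.2 mg start would still leave Level -1 equal to it.

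A reader might also infer that the Grade 2 rash row orders a second, impermissible reduction. The row does reduce at once and, if there is no recovery in 2 weeks, interrupts and restarts at the next lower dose. But its two outcomes can be read as alternatives after a trial reduction: back up to the previous dose on recovery, or restart below that previous dose otherwise. The single-reduction rule in 2.1, the one lower level in Appendix II and the one-level reduction on resuming in 10.10 all point to a restart at Level -1. The documents therefore show loose wording, not an order for an unlisted dose.

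**Conclusion.** The table error holds and is exact. Two of 14 oral-solution rows print a Level -1 that is not a reduction: +50% in mg at 9.0-9.9 kg and 0% at 10.0-10.9 kg. First reductions from Level 1 at 11 kg and above work as printed. Separately, any subject on 0.0125 mg/kg has no printed lower level.

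Harm at 9.0-9.9 kg needs two conditions: the infant is on the 0.0125 mg/kg start, and the site follows the cell over the words of the toxicity rule. It would go too far to say that sites will give the higher dose. The documents do not give the number of subjects in these bands or on the low start, so the number affected is unknown. The matter is one of dosing safety and should be fixed. The rash wording is a minor clarification.

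**What to change.** One amendment to Appendix II and one sentence in 10.2.6.3:

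- **10.0-10.9 kg:** correct Level 1 to the header rate, 0.025 x 10 = 0.25 mg (5 mL), and keep Level -1 at 0.2 mg, a 20% cut. If 0.2 mg is the intended start, print a lower Level -1 instead. The first option raises the starting dose by 25% (0.25/0.2) and gives the same Level 1 as the 11-11.9 kg row, so the sponsor should confirm the intent.
- **9.0-9.9 kg:** separate the 0.0125 mg/kg start from a 0.025 mg/kg start, and keep 0.18 mg only as the reduction from 0.025 mg/kg. Change 2.3 mL to 2.4 mL so that it matches 0.12 mg and the 4.3.1 rounding rule.
- **Note for all weights:** a subject on 0.0125 mg/kg who needs a reduction either discontinues or goes to a lower printed dose set by the sponsor, never to 0.020 mg/kg. The table's own ratio, 0.020/0.025 = 0.8, would give 0.010 mg/kg. At 9.0-9.9 kg that is 0.09 to 0.10 mg, about 1.8 to 2.0 mL.
- **Grade 2 rash row:** state that restart after non-recovery is at Dose Level -1, and that a further need for reduction means discontinuation.

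The changes add no visits or staff. The cost is that a few subjects who might tolerate a dose below Level -1 would stop. The protocol gives no supporting data for a dose below 0.0125 mg/kg, so the sponsor may prefer discontinuation there.
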